Health Care Utilization	Caregiver interview – health care utilization survey Review of medical chart and pharmacy records	Baseline, each follow-up Conclusion of Study
Airway Inflammation	Objective measurement: FeNO	Baseline, follow-up 2, final
Pulmonary Function	Spirometry	Baseline, follow-up 2, final
Functional Outcomes		
School Absenteeism	Caregiver interview School record review	Baseline, each follow-up Conclusion of study
Quality of Life	Caregiver interview-PACQLQ	Baseline, each follow-up
Potential Mediators		
Adherence	Caregiver interview- Horne Adherence Scale Pharmacy Data	Baseline, each follow-up End of study
Communication with Providers	Caregiver interview-PEPPI	Baseline, final
Satisfaction with Medical Care	Caregiver interview-PSQ-18	Baseline, final
Independent Variables		
Demographic, Medical Variables	Caregiver interview	Baseline
Caregiver Depression*	Caregiver interview-CES-D	Baseline, final survey
Environmental Allergens	Environmental survey	Baseline
Secondhand Smoke	Caregiver interview Salivary Cotinine measurement	Baseline, each follow-up Baseline, final
Process Evaluation		
Training of School Nurses, CTAs, and Providers	Time to train nurses to deliver DOT with proper inhaler technique, train CTAs for asthma assessments, and providers for reinforcement of guideline based asthma care	Tracking logs for entire study period
Medication Delivery to School	Tracking log of days required to deliver medications to school and home and initiate DOT; both at beginning of the study and for follow-up adjustments	Treatment group only – tracking log
Percent of Days Children Receive Medications via DOT	Nurse medication administration logs	Treatment group only – collected at the end of the school year
Diffusion of Innovations Summary Measures Relative Advantage, Compatibility, Simplicity, Trialability, Observable Results	Semi-structured interview: parents, nurses, administrators, PCPs Perceived Attributes scale ¹² (for school nurses, health aides, and administrators)	At conclusion of study

*All Families will be provided a list of local mental health resources at the beginning of this study.

Fraction of Exhaled Nitric Oxide (FeNO):

Fraction of Exhaled Nitric Oxide (FeNO) measurement is a non-invasive measure of lung inflammation. This inflammation could be caused by many factors including colds, pollutant exposures, and asthma. FeNO will be measured using the NIOX MINO® Airway Inflammation Monitor, an electrochemical hand-

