The primary analysis of this study aims to assess the effectiveness of the SB-TEAM intervention in reducing asthma morbidity (including symptom-free days post-intervention (follow-ups at 4 mo, 6mo and final) as the primary outcome) compared to an enhanced usual care comparison group in school age children with persistent asthma. We will follow subjects prospectively throughout the school year for clinical outcomes (symptoms, asthma control, health care use), functional outcomes (absenteeism, quality of life), and airway inflammation (FeNO). We will use graphical and numerical summaries to describe the outcomes at each assessment point. If distributional assumptions associated with a particular statistical procedure are violated, appropriate transformations will be made or non-parametric alternatives will be used. In accordance with the intention-to-treat principle, all randomized subjects will be analyzed within the group to which they were assigned; minimal crossover is expected. Hypothesis-driven comparisons will be made to control the family-wise type I error rate at 0.05 (two-sided) for the primary hypothesis.

We will determine whether there are important differences at baseline despite randomization between the SB-TEAM and eUC groups in demographics and background characteristics (age, race, ethnicity, insurance, caretaker education), depression, and cotinine. This will include t-tests (or Wilcoxon Rank Sum test) for continuous variables and chi-square (or Fisher's Exact) tests for discrete variables. These comparisons will enable the identification of control variables for use in analyses evaluating treatment effect.

To test for differences between the SB-TEAM and eUC groups on clinical and functional outcomes at the primary time point, bivariate comparisons will be made using t-tests for continuous variables (number of symptom-free days (SFD), symptom nights, rescue medication use, days absent, quality of life, FeNO,

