We will also consider whether certain process measures from our conceptual framework (adherence, patient/provider communication, satisfaction with medical care) act as mediators in the relationship between the intervention and outcomes. Thus we will estimate both the direct intervention effect on the outcomes, as well as the indirect effect through process mediators. For each purported mediator, we will use structural equation models (SEM) to model its relationship to treatment and primary outcome. SEM can quantify both direct relationships between latent traits, the effects of factors that modify these relationships, and also indirect relationships mediated by other factors. Potential confounders such as baseline symptoms will be included as covariates. Maximum Likelihood (ML) will be used for estimation. Goodness-of-fit will be assessed in a two-level process. In the first level, the fit of the unrestricted model will be tested using standard diagnostic measures for linear regression. In level two, the appropriateness of assumption of the proposed structural equation model will be investigated by testing this model against the unrestricted model. The following indicators will be used: (a) Comparative Fit Index (CFI), (b) Non-Normed Fit Index and (c) Root Mean Square Error of Approximation. We will use chi-square statistics for the structural invariance tests to determine effect modifiers. These analyses will aid in our understanding of pathways by which SB-TEAM impacts outcomes.

The primary analyses will be performed according to the intention-to-treat principle and will include all randomized subjects. Substantial attention will be invested in participant retention; reasons for any subject withdrawals that may occur will be carefully documented. Missing data patterns will be examined by comparing subjects who discontinued with those who remained in the study. Inference based on the proposed methods GEE and/or LMM is valid provided that missing data follows the missing completely at random (MCAR) assumption. However, if the occurrence of missing data depends on the observed response but is independent of unobserved data (MAR), weight GEE (WGEE) will be used. Sensitivity analysis to MAR assumption will also be carried out.

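### Communication and satisfaction are measured after randomization only at the final visit, so the planned mediation models cannot tell mediation from better symptoms improving caregiver ratings

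*Combined protocol and SAP*

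**What the plan says.** The mediation paragraph in section 11 (Primary Analysis) asks whether three process measures ("adherence, patient/provider communication, satisfaction with medical care) act as mediators in the relationship between the intervention and outcomes"). It intends to estimate both a direct effect and an indirect effect through each, and commits to a method: "For each purported mediator, we will use structural equation models (SEM) to model its relationship to treatment and primary outcome". Covariates are to include potential confounders, with baseline symptoms as the example. Model fit is judged by CFI, the Non-Normed Fit Index and RMSEA.

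The section 5 Measures table lists the mediators' schedules:
- Communication: "Caregiver interview-PEPPI Baseline, final".
- Satisfaction: "Caregiver interview-PSQ-18 Baseline, final".
- Adherence: the Horne scale and pharmacy data, at "Baseline, each follow-up End of study" respectively.

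Section 11 defines the primary outcome as "symptom-free days post-intervention (follow-ups at 4 mo, 6mo and final"). Under section 4, caregivers are telephoned every other month, and a home visit closes the school year.

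**The concern.** A mediator has to change before the outcome it is said to explain. PEPPI and PSQ-18 each have one value after randomization. It comes later than two of the three outcome visits and at the same visit as the third. A caregiver whose child improved by month 4 or 6 may well rate communication and care more favourably at the end of the year. Because the intervention is expected to improve symptoms, treatment would then be associated with the rating, and the rating with SFD. Those are the two paths that a mediation model multiplies into an indirect effect.

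The plan wants this analysis to show how the program works. A false mediator would misdirect the choice of which parts of a multi-component program to keep.

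**Working it through.** **1. Timing, set side by side.**

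| Outcome visit for SFD | Position of the only post-randomization PEPPI and PSQ-18 |
|---|---|
| 4 months | after the outcome |
| 6 months | after the outcome |
| Final | same visit |

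No row has the mediator first, so the result does not depend on which visits enter the model.

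**2. Does the plan repair this?** Adjusting for baseline symptoms does not block a path from 4- or 6-month symptoms to the final rating. No lag, time-ordering rule or reverse-path model is given. The fit indices cannot settle direction, because a model with the arrow reversed can fit equally well. The stated sensitivity analysis concerns missing data (MAR) only.

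**3. The plan's own figure.** The plan gives no figure for mediation, but its sample size supplies the inputs: SD 2.8, within-subject correlation 0.3, difference 0.8, two assessments, 90% power, two-sided 0.05.
- SD of the mean of two assessments: 2.8 × √((1 + 0.3)/2) = 2.257.
- Per arm: 2 × (1.960 + 1.282)² × 2.257² / 0.8² ≈ 167.3, so 168.
- The total of 336 agrees with the plan; power at 168 per arm is 90.1%.

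**4. Size of the possible error.** Assume no true mediation. Let the final rating be M = r × S + √(1 − r²) × e. Here S is the mean of 4- and 6-month SFD divided by 2.257, and e is standard normal noise. The correlation r is an assumption. So are normality, the same SD and correlation 0.3 for baseline SFD, and the joint-significance rule (both paths significant at 0.05).

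Share of the treatment effect credited to M:
- Treatment to rating: a = r × 0.8/2.257 = 0.354r.
- Visit variance is 2.8² = 7.84 and between-visit covariance is 0.3 × 7.84 = 2.352. Adjusting for baseline SFD removes 2.352²/7.84 = 0.706 from each, leaving 7.134 and 1.646.
- The residual variance of the 4- and 6-month mean is (7.134 + 1.646)/2 = 4.390. Its covariance with the three-visit mean is (2 × 4.390 + 1.646)/3 = 3.476, and with final SFD 1.646.
- The residual variance of M is 1 − r²(1 − 4.390/5.096) = 1 − 0.138r².
- Rating to outcome: b = r × (3.476/2.257)/(1 − 0.138r²) for mean SFD. For final SFD, 1.646 replaces 3.476.
- Share = a × b/0.8, which is 0.682r²/(1 − 0.138r²) for mean SFD and 0.323r²/(1 − 0.138r²) for final SFD.

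Simulation with 168 per arm and baseline SFD adjusted gives the false-mediation rates:

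| r (assumed) | Share, mean SFD | False mediation, mean SFD | Share, final SFD | False mediation, final SFD |
|---|---|---|---|---|
| 0.2 | 2.7% | about 9% | 1.3% | about 2% |
| 0.3 | 6.2% | about 15% | 2.9% | about 4% |
| 0.4 | 11.2% | about 24% | 5.3% | about 12% |
| 0.5 | 17.7% | about 36% | 8.4% | about 26% |

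The simulated shares run from about 3% to 17% and from about 1% to 8%, in line with the formula. Repeat simulations move the rates by one or two points. At r = 0 the rate is about 0.2%.

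The final-SFD columns assume that symptoms at the final visit do not themselves affect the rating given then. If the rating instead follows SFD over all three visits, the final-only rates are 7.5%, 17.5% and 45.9% at r = 0.2, 0.3 and 0.5.

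**5. Would an earlier questionnaire help?** Simulate a 4-month rating driven only by 4-month SFD, with mean SFD at 6 months and final as outcome. Adjusting for baseline SFD alone, false mediation is still about 2%, 4%, 10% and 19% at r = 0.2 to 0.5. Adding 4-month SFD to the outcome model brings it to 2% or less throughout.

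**The case against.** The strongest reply is that this analysis is supportive. The plan introduces mediation as something it will also consider, does not list it among the study objectives, and limits family-wise error control to the primary hypothesis. That stands, and it sets the priority low. It does not remove the point, because the plan still commits to an indirect effect that its schedule cannot identify.

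A second reply is that the harm is conditional. A reader might infer that the model will count symptom-driven satisfaction as mediation. The documents do not support that: they give no correlation between symptoms and these ratings, and at 0.2 or below the credited share is about 3% or less.

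A third is that the model is not specified. A reader might assume that the final rating is set against all three outcome visits, but the plan does not say so. Under the same mechanism, final SFD alone gives lower figures. That reply affects the size only, since even there mediator and outcome are concurrent.

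Finally, adherence, which directly observed therapy targets most directly, is self-reported at each follow-up and can be placed before a later outcome. The problem does not extend to that measure.

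**Conclusion.** The point holds for PEPPI and PSQ-18. Neither can be placed before any primary-outcome visit, so an indirect effect through them cannot be distinguished from symptoms influencing ratings. This follows from the schedule alone.

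The size rests on the assumed correlation of 0.2 to 0.5, the assumed joint-significance rule and no true mediation. The false-mediation rate is then about 9% to 36% with mean SFD (about 3% to 17% of the effect credited to the mediator). With final SFD only it is about 2% to 26% (about 1% to 8% credited).

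A reader might go on to doubt the trial's main result. Nothing here supports that: the primary comparison and the sample size are untouched. This is a cheap improvement of lower priority.

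**What to change.** Add PEPPI and PSQ-18 at follow-up 2 (4 months), an existing contact where the ACT and FeNO are already collected. State in section 11 that these mediation models use the 4-month mediator and SFD at 6 months and final, adjusted for the baseline mediator, baseline SFD and 4-month SFD. The last covariate is essential, because moving the questionnaire without it leaves much of the bias. Say openly that this mediation outcome leaves out the 4-month visit of the primary outcome. Treat self-reported adherence the same way; it needs no new data collection.

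The cost is two short questionnaires at one contact and a few sentences of analysis text. Adjusting for 4-month SFD also gives up any indirect effect already complete by month 4.

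If the schedule cannot change, report the PEPPI and PSQ-18 results as associations with SFD, not as mediation or indirect effects. That needs wording only.

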Once randomized, the study coordinator will use the web-based system or fax to send a symptom report from the screening assessment and notification of enrollment in the study to the child's primary care provider (PCP). This report will include an explanation of the processes of the SB-TEAM program and will advise them to continue to care for the child's healthcare needs as usual. In collaboration with the telemedicine program, the study team will schedule children in the SB-TEAM group for a telemedicine visit in the school health office at the start of the school year (within 2 weeks of the baseline visit) to provide an initial assessment and determine the starting medication to be used for directly observed therapy. Telemedicine is established in the Rochester City Schools, and is currently used for acute care (i.e. illness visits for ear pain, sore throat, rashes) as well as chronic care (ADHD, asthma). We will incorporate the process for this study into the standard telemedicine system, to assure appropriate medical assessment and follow-up for guideline based asthma care delivery. Appointments for all visits are scheduled in conjunction with the child's caregiver, who may join the child at school for the visit if desired. The school site portion of the visit will be completed by certified telemedicine assistants (CTAs) who already work in the district. As per the 'usual' telemedicine protocol in the schools, the CTA will bring the mobile telemedicine unit and meet with the child at school, will enter information regarding the child's symptoms and

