Three main categories of costs to be considered include programmatic costs, productivity costs, and medical costs estimated at the individual child level. Programmatic costs include costs of initiating and running the program, hiring and training staff, purchasing or leasing equipment, staff travel, and information system costs. Costs associated with this study that would not exist as part of the intervention will not be included, as we do not anticipate that they would continue beyond the duration of the study. Per person programmatic costs will be calculated by dividing the total costs of the program by the total number of children with persistent asthma in the schools. We will determine *productivity/opportunity costs* based on the amount of time parents take from work to care for sick children or take them to a doctor. Time from work will be valued at the median of the pay scale estimates based on age, race and gender specific wages from the Bureau of Labor Statistics. We will assess the impact of the intervention on *medical* costs using parent-reported health services use data and medical record review. We will ask parents at each follow-up about their child's ER or physician visits, hospitalizations, medical procedures, use of medications and durable equipment. Healthcare use will be converted to costs using the NYS Medicaid fee schedule and other sources. Annual medical costs per person will be analyzed using a 2-part model to adjust for zero expenses in a given year. All costs will be adjusted to the last year of the intervention using the appropriate component of the Consumer Price Index (CPI).

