We will consider the total costs of initiating and maintaining the program as well as the incremental cost-effectiveness ratio (ICER) of the SB-TEAM vs. eUC, which is the ratio of differences in costs between the 2 study groups to the difference in the number of symptom-free days (SFD) gained between the 2 groups. The main outcome for the analysis from the societal perspective will be an incremental cost-effectiveness ratio (ICER), which is the ratio of net program costs to the number of symptom-free days (SFD) gained, $ICER = (\Delta Medical + \Delta Productivity + \$Program) / \Delta SFD$, where $\Delta = (SB-TEAM) - (eUC)$. We will bootstrap the ICER to estimate standard error and to evaluate the uncertainty around the point estimate. The ICER will be compared to similar estimates from the literature. An acceptability curve, linking various values of 1 SFD to the probability of SB-TEAM being cost-effective, will be plotted. The study from the Medicaid perspective will use the cost-benefit approach to economic evaluation. Benefits will be described as the net difference in medical and productivity costs between children in the SB-TEAM and eUC groups. The cost is equivalent to the cost of the program. Equation: *Net Monetary Benefit* = $\Delta Medical - \$Program$.

Process Evaluation: Descriptive statistics will be used for the process evaluation, looking in particular at the efficiency of the program implementation along with the responses from parents, primary care providers, and school nurses and administrators about convenience, scheduling, satisfaction, and sustainability.

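### The program-cost term in the ICER is averaged over all children with persistent asthma in the schools and carries no between-arm difference, so it matches the other terms only under conditions the plan does not state

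*Combined protocol and SAP*

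**What the plan says.** Section 11, Cost Effectiveness Analysis, has three cost categories: programmatic, productivity and medical. Programmatic costs cover starting and running the program, staff and their training, and "purchasing or leasing equipment, staff travel, and information system costs". There is one exclusion: "Costs associated with this study that would not exist as part of the intervention will not be included". The per-person programmatic cost is then "calculated by dividing the total costs of the program by the total number of children with persistent asthma in the schools".

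The ICER is described twice in words. It is first a ratio of SB-TEAM against eUC, "which is the ratio of differences in costs between the 2 study groups" to the difference in SFD. For the societal perspective it is a ratio "which is the ratio of net program costs to the number of symptom-free days (SFD) gained". The printed formula is (ΔMedical + ΔProductivity + `$Program`) / ΔSFD, with Δ meaning SB-TEAM minus eUC. There is no Δ on `$Program`. The Medicaid analysis uses ΔMedical − `$Program` and states: "The cost is equivalent to the cost of the program".

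Section 3 (Randomization) plans 200 children per arm. For SB-TEAM, "the study coordinator will use the web-based system or fax to send a symptom report from the screening assessment" to the primary care provider. The eUC subsection uses the same web-based system or fax for its own report. It also gives eUC families and providers feedback on the timetable of the SB-TEAM telemedicine visits.

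**The concern.** The terms added together do not obviously refer to the same children or to the same contrast.

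- **Denominator.** ΔMedical, ΔProductivity and ΔSFD are per-child contrasts among randomized children. The program term is an average over every child with persistent asthma in the schools. If the costed program serves fewer children than are counted, its cost per child is diluted while its effect per child is not.
- **Contrast.** The verbal definition asks for a difference between the two groups. The formula takes no difference on the program term, and nothing says that components also supplied to eUC are removed.

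Cost-effectiveness is objective 6 of the study. The same term enters the base-case ICER, the acceptability curve and the Medicaid net benefit. Because it is a single average, bootstrapping children would not expose an error in its denominator or scope.

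**Working it through.** **1. The plan's own count.** Section 11, Sample Size, gives 11,000 students plus 6,600 kindergarten entrants, 9% asthma prevalence, and about half of cases persistent:

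(11,000 + 6,600) × 0.09 = 1,584; 1,584 × 0.5 = 792.

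Both printed figures are reproduced. The same section equates 120 children a year with 60%, which implies 120/0.60 = 200 eligible a year, or 800 over the four recruitment years. So 792 is compatible with a pool for the whole trial and can be set against the 200 children planned for SB-TEAM over the same period.

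**2. Effect of the denominator.** Let C be total program cost, N the children counted and M the children served by the program whose cost is C. The plan uses C/N. The figure matched to a per-child effect is C/M. The written term is too small by the factor N/M.

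| Meaning of C | N/M | Written term as share of C/M |
|---|---|---|
| Cost as delivered in the trial | 792/200 = 3.96 | 25% |
| District-wide cost, 60% uptake | 1/0.60 = 1.67 | 60% |
| District-wide cost, 74% uptake | 1/0.74 = 1.35 | 74% |
| District-wide cost, full coverage | 1.00 | 100% |

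The 60% and 74% are the planned and prior-study research enrollment rates in Sample Size. They are borrowed here as assumed uptake; the documents give no uptake figure for a routine program.

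**3. Effect of the missing difference.** Let E be the part of C to be taken off to reach the increment over eUC: components common to both arms, plus the cost of eUC feedback. The matched increment is (C − E)/M. This is smaller than C/M, so omitting the subtraction raises the program term and works against SB-TEAM. The two effects cancel when

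C/N = (C − E)/M, that is E/C = 1 − M/N.

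This is 1 − 200/792 = 75% for a trial-delivered total, 40% at 60% uptake, 26% at 74% uptake, and 0% at full coverage. The documents give no value for E, so this effect cannot be sized.

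**4. Carry-over to the ICER.** These factors apply to `$Program` alone. The ICER changes by the same factor only if ΔMedical + ΔProductivity is zero. No program cost is given, so no dollar error can be stated.

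**The case against.** The strongest reply is that this is a roll-out cost. Objective 6 and the opening of the Cost Effectiveness Analysis stress sustainability and dissemination. Study-only costs are dropped because they would not continue after the study. On that reading, dividing by all affected children is natural. This has real textual support, but the plan never says the total is district-wide, and the match is exact only at full coverage.

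On the missing Δ, the verbal definitions speak of differences between groups and of net program costs. If `$Program` means SB-TEAM-only cost, its eUC value is zero and no Δ is needed. That softens the point. Still, the section defines the term from total program cost, counts information systems in it, and gives no netting rule. The exclusion of study-only costs does not help, because a reporting system used in both arms is part of the intervention.

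Two further replies stand in part. Screening reaches children who never receive treatment at school, so for that component a wider denominator is defensible. And a trial-volume figure has its own distortion: 200/4 = 50 SB-TEAM children a year, across about 60 or more schools, would carry near-fixed costs. Which figure should be the base case is therefore a matter of judgement.

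The plan also says: "We will consider the total costs of initiating and maintaining the program". If the totals are reported, a reader could apply another denominator, but the ICER and net benefit would remain as defined.

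**Conclusion.** The concern holds in a conditional form. The stated denominator need not match its numerator, and the formula does not visibly carry out the plan's verbal definition of the ICER. Before any shared cost is netted out, the program term is understated by roughly 3.96 if the total is trial-delivered cost, by 1/uptake if it is district-wide with incomplete uptake, and not at all at full coverage. The 3.96 rests on a planning count and a planned arm size and is indicative only.

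A reader might infer three stronger conclusions that the documents do not support:

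- **That the ICER is fourfold too low.** The factor applies to one term and to one reading of the total. Telemedicine visits and medications are billed to insurance (section 3), so much of the intervention's cost may sit in ΔMedical.
- **That shared costs will certainly be charged to SB-TEAM.** The plan does not say so; it only fails to rule it out.
- **That the analysis is biased toward SB-TEAM overall.** The two effects oppose each other. For a trial-delivered total, 75% of program cost would have to be netted out before they cancelled. For a district-wide total the net direction is not established.

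The primary SFD comparison is unaffected.

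**What to change.** In section 11, Cost Effectiveness Analysis:

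1. State what the total program cost covers, and divide it by the number of children served by that same program. For the trial-based ICER this is the children assigned to SB-TEAM (200 planned). Define what being served means for screening as distinct from treatment at school.
2. Define `$Program` as the increment over eUC, with components common to both arms netted out and the cost of eUC feedback credited to eUC. Use this in the ICER, the acceptability curve and the Medicaid net benefit.
3. Report a trial-volume ICER and a labelled roll-out ICER. The latter needs its own total cost at that volume and a range of uptake, for example 60%, 74% and 100%. State in advance which is the base case.

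No new subject data are needed. Program costs must be allocated by arm. The process-evaluation logs in section 5 cover training time and medication delivery but do not split coordinator or information-system effort between arms, so some allocation will rest on assumption and should be varied. The trial-volume figure may overstate routine cost per child, because fixed costs fall on about 50 SB-TEAM children a year; the roll-out figure answers that. The reported ICER may look less favourable to SB-TEAM.
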